2.3 PK endpoint

1) Tears collection for Lubricin dosing.

3 INVESTIGATIONAL PLAN

3.1 Overall investigation design

A 2 week randomized (1:1:1), controlled, double-masked, parallel group, pre-market study.

Patients with ocular discomfort following refractive surgery procedure (within 6 months from enrollment into the investigation) will be evaluated at baseline (Day 1), at Week 2 (day 15±2 days) and at Week 3 follow-up visit (day 22±2, or early exit).

3.2 Discussion of design

The investigation has been designed in agreement with the ICH E6 (R1) and ISO14155-2012 guidelines (1, 4).

The aim of the investigation is to evaluate tolerability, safety permanence on the ocular surface and efficacy of two concentrations of Lubricin (20 and 50 µg/mL) eye drops versus sodium hyaluronate (HA) 0.18% eye drops (Vismed®) in patients with ocular discomfort following refractive surgery.

Enrolled subjects will be randomized at inclusion, 1:1:1 ratio to receive Lubricin 20 µg/ml eye drops solution or Lubricin 50 µg/ml eye drops solution or sodium hyaluronate (HA) 0.18% eye drops solution. Upon randomization and until the end of the treatment period, subjects will be required to not use topical ophthalmic medications except of the study treatments. On the Day 1 Visit (Baseline visit) subjects will be dispensed of the study medication and instructed to self-administer at home three times a day approximately every 6 hours for 2 weeks.

Subjects will be evaluated after 2 weeks of treatment and 1 week after end of treatment. The subjects will be involved in the study for a maximum of 25 days from screening visit to last follow-up visit.

4 INVESTIGATION POPULATION

4.1 Target population

Subjects suffering of ocular discomfort following refractive surgery.

4.2 Investigation population

All subjects suffering of ocular discomfort following refractive surgery who are already under treatment at the Policlinico Umberto I or who are diagnosed as being affected of ocular discomfort following refractive surgery during a visit at the Policlinico Umberto I.

4.3 Method of sampling

The investigation sample is the sample of subjects chosen from the investigation population that are included into the investigation.

A simple random sampling strategy was used in this investigation.

All eligible subjects willing to participate to the investigation were included.

4.4 Inclusion criteria

1. Patients 18 years of age or older.
2. Patients undergone ocular refractive surgery within 6 months from Day 1 Visit.
3. Patients with ocular discomfort defined as SANDE score ≥ 30 at baseline.
4. Average VAS score (dryness, foreign body sensation, burning/stinging, itching, pain, stick feeling, blurred vision and photophobia) ≥ 25 mm;
5. Best corrected distance visual acuity (BCDVA) score ≥ 0.1 decimal units in both eyes at the time of study enrolment.
6. Only patients who satisfy all Informed Consent requirements may be included in the study. The patient and/or his/her legal representative must read, sign and date the Informed Consent document before any study-related procedures are performed. The Informed Consent form signed by patients and/or legal representative must have been approved by the IEC for the current study.

4.5 Exclusion criteria

1. Patients with a severe Dry Eye condition (intensity level 4 according to the Report of the International Dry Eye Workshop -DEWS, 2007)
2. Best corrected distance visual acuity (BCDVA) score of < 0.1 decimal units in either eye at the time of study enrolment
3. Evidence of an active ocular infection in either eye
4. History or presence of ocular surface disorders other than ocular discomfort in either eye

5. Use of any ocular topical medication other than the study medications for the treatment of ocular diseases including artificial tears during the study period
6. Use of topical cyclosporine, topical corticosteroids or any other topical medication for the treatment of dry eye in either eye within 30 days of study enrolment
7. History of any ocular surgery (excluding laser or refractive surgical procedures) in either eye within 30 days before study enrolment. Ocular surgery will not be allowed during the study treatment period and elective ocular surgery procedures should not be planned during the duration of the follow-up period
8. Known hypersensitivity to one of the components of the study or procedural medications
9. Participation in another clinical study at the same time as the present study or within 90 days of screening/baseline visit
10. History of drug, medication or alcohol abuse or addiction.
11. Females of childbearing potential (those who are not surgically sterilized or post-menopausal for at least 1 year) are excluded from participation in the study if they meet any one of the following conditions:
 - a. are currently pregnant or,
 - b. have a positive result on the urine pregnancy test at the Screening/Baseline Visit or,
 - c. intend to become pregnant during the study treatment period or,
 - d. are breast-feeding or, not willing to use highly effective birth control measures, such as: Hormonal contraceptives – oral, implanted, transdermal, or injected and/or mechanical barrier methods – spermicide in conjunction with a barrier such as a condom or diaphragm or IUD during the entire course of and 30 days after the study treatment periods.

4.5.1 Not allowed treatments

Use of topical cyclosporine, topical corticosteroids or any other topical medication for the treatment of dry eye in either eye is not allowed during the treatment period.

During the study follow-up period (from day 15±2 to day 22±2), any ocular topical treatments are allowed, including other artificial tears/lubricants as prescribed by the treating physician.

Hormonal contraceptives for females will be allowed.

5 INVESTIGATION SCHEDULE

The schedule of the investigation is summarised at page [5](#).

5.1 Investigation visits and procedures

A written informed consent will be obtained before any study assessment or procedure. Maximum study duration will be 25 days, including all study visits.

Each study subject will undergo to 3 visits.

The first subject first visit (FSFV) is defined as the 1st visit performed at the clinical site by the 1st enrolled subject. The last subject last visit (LSLV) is defined as the last visit performed at the clinical site (or the telephonic follow-up, if applicable) by the last subject, i.e. the last visit foreseen by the study protocol, independently of the fact that the subject is a completer or a withdrawn subject.

The following phases, visits and procedures will be performed:

- **Interventional phase**
 - Visit 1 - Day 1
 - Visit 2 - Day 15 ± 2
- **Follow-up phase**
 - Visit 3 - Final Visit follow-up - (Day 22±2) /ETV (Early Termination Visit) in case of early discontinuation, discontinued subjects will undergo an early termination visit (ETV).

The procedures/assessments details are summarized hereafter.

	Day	Procedures/Assessments
Visit 1 – Day 1 – Baseline – Pre-Dose	Day 1 pre-dose	
 ➤ Explanation to the patient of study aims, procedures and possible risks ➤ Informed consent signature ➤ Screening number (as S01, S02, etc.) ➤ Demographic data ➤ Medical and surgical history/current medical conditions ➤ Prior/concomitant medications ➤ External Ocular Examination ➤ AE monitoring ➤ Ocular examination in both eyes: 
 1. Assessment of ocular tolerability (Visual analogue scale, VAS: dryness, foreign body sensation, burning/stinging, itching, pain, stick feeling, blurred vision and photophobia) 2. Assessment by SANDE questionnaire 3. Assessment of best corrected distance visual acuity 4. Slit lamp examination (SLE) to assess the Eyelid - Meibomian glands, Eyelid Erythema, Eyelid – Oedema, Lashes, Conjunctiva Erythema, Lens, Iris, Anterior Chamber, Corneal transparency, Corneal neovascularization 5. Assessment of central corneal sensitivity by Cochet-Bonnet aesthesiometry 6. Tear collection for Lubricin dosing (both eyes) using tear wash technique with 40 µL of sterile saline solution 
At least 10 minutes break
 
 7. Tear Film Break Up Time (TFBUT) 8. Corneal fluorescein staining (Oxford score) 
At least 15 minutes break
 
 9. Schirmer's test (ST) I (without anaesthesia) 10. Intraocular pressure (IOP) 
 ➤ Pregnancy test for female patients. ➤ Inclusion/exclusion criteria evaluation ➤ Patient eligibility confirmation and randomization number assignment ➤ At the completion of the pre-dose assessments, the investigator will administer the study product (morning dose) into the eligible eye(s)
Baseline - Visit 1	Day 1 15 minutes post-dose	
The following procedures will be performed:
 
 ➤ Assessment of ocular tolerability (Visual analogue scale, VAS: dryness, foreign body sensation, burning/stinging, itching, pain, stick feeling, blurred vision and photophobia) ➤ Tear collection for Lubricin dosing in the right eye

	Day	Procedures/Assessments
Baseline - Visit 1	Day 1 30 minutes post-dose	
The following procedures will be performed:
 
 ➤ Assessment of ocular tolerability (Visual analogue scale, VAS: dryness, foreign body sensation, burning/stinging, itching, pain, stick feeling, blurred vision and photophobia) ➤ Tear collection for Lubricin dosing in the left eye ➤ The Investigator will deliver to the patients the investigational medical device for the treatment period (15±2 days)
At home	From Day 1 to Week 2± 2 Days Visit	
 ➤ Self-administration at home of the Investigational medical device TID approximately every 6h into the eligible eye(s)
Visit 2	Week 2 ± 2 Days (prior the morning dose)	
The following procedures will be performed before receiving the first eye drop treatment of the day:
 
 ➤ Review of current medical conditions (ocular and systemic: including External Ocular Examination) ➤ AE and concomitant medications ➤ Ocular examination in both eyes, consisting of the assessments detailed for the baseline visit (points 1-10), in the same order and with the same intervals ➤ Urine Pregnancy test (only female) ➤ At the completion of the pre-dose assessments, the investigator will administer the study product (morning dose) into the eligible eye(s)
Visit 2	Week 2 ± 2 Days 15 minutes post-dose	
The following procedures will be performed:
 
 ➤ Assessment of ocular tolerability (Visual analogue scale, VAS: dryness, foreign body sensation, burning/stinging, itching, pain, stick feeling, blurred vision and photophobia) ➤ Tear collection for Lubricin dosing in the right eye
Visit 2	Week 2 ± 2 Days 30 minutes post-dose	
The following procedures will be performed:
 
 ➤ Assessment of ocular tolerability (Visual analogue scale, VAS: dryness, foreign body sensation, burning/stinging, itching, pain, stick feeling, blurred vision and photophobia) ➤ Tear collection for Lubricin dosing in the left eye

Visit 3/ETV Final Follow-Up Visit	Day Days 22 ± 2	Procedures/Assessments
		
The final visit is defined as the visit performed 7 ± 2 days after last administration (day 21 ± 2). In case of study discontinuation subjects will undergo an early termination visit.
 
The following procedures will be performed:
 
➤ Review of current medical conditions (ocular and systemic: including External Ocular Examination)➤ AE and concomitant medications➤ Ocular examination in both eyes, consisting of the assessments detailed for the baseline visit (points 1-10), in the same order and with the same intervals➤ Patient discharge

6 INVESTIGATION SUBJECT IDENTIFICATION METHOD AND TREATMENT ASSIGNMENT METHOD

6.1 Unique subject identifier

All the subjects who sign the informed consent form for the present study will be coded with “unique subject identifiers” when data are extracted from the study database into the domains of the CDISC SDTM model. The unique subject identifier for study site consists of the Sponsor study code (i.e. LUB0116MD), the 3-digit screening number (e.g. S01, S02, etc.) and, if applicable, the 2-digit subject study number (e.g. 01, 02, etc.). Study code, screening number and subject study number are separated by slashes (e.g. “LUB0116MD/S01/01”).

6.2 Subject identifier for the investigation

The last 5 digits of the unique subject identifier (randomized subjects), corresponding to the subject screening and subject study numbers separated by a slash, or the last 3 digits of the unique subject identifier (not randomized subjects), corresponding to the subject screening number, will appear as subject identifier in the individual listings and figures of the clinical study report and will be used to identify the subjects in in-text tables or wording (if applicable).

6.3 Randomization

The randomization list was computer-generated by the CRO Biometry Unit, using the PLAN procedure of the SAS® version 9.3 (TS1M1) (6) according to the following specification:

- Randomization scheme: 1:1:1
- Block size: 6
- Stratification factors: None

The randomization list will be attached to the final clinical study report.

6.4 Treatment allocation

Subjects were assigned to the treatment arms according to the randomization list.

Randomization numbers were given to the subjects on study day 1 and were used to assign the treatment arms according to the randomization list.

6.5 Blinding

This is a double blind study. Both the investigators and the subjects are not aware of the treatment administered.

Individual envelopes identified with the subject assignment number were prepared. Each one includes the treatment arm assigned to each subject. These envelopes, duly closed and sealed, are included into the Investigator File (IF).

During the study the integrity of the envelopes was regularly checked by CRO Monitor during the visits at site. At the end of the study all the individual envelopes must be returned to Dompé.

The sealed envelope can only be opened in case of emergency, when knowledge of the treatment arm is essential for treating the subject.

Only in case of real need the Investigator may open the sealed envelope. In case of opening, all the details (date, time, reasons....) must be specified into the CRF and the Sponsor must be informed within 24 hours.

If an envelope is opened before the end of the trial, the subject is excluded from the trial.

Copies of the individual envelopes identified with the subject assignment number were also sent to the Dompé Materiovigilance Responsible. Dompé Materiovigilance unblinds a patient treatment arm only for safety reason and documents envelope opening; unblinding is not mandatory before regulatory submission of a reportable SAE/Investigational Medical Device Deficiency.

7 INVESTIGATION EVALUATION PARAMETERS

7.1 Efficacy parameters

7.1.1 Primary efficacy parameters

- Visual analogue scale (VAS) for dryness, foreign body sensation, burning/stinging, itching, pain, stick feeling, blurred vision and photophobia.

7.1.2 Secondary efficacy parameters

- Ocular surface vital staining with Fluorescein (Oxford scale);
- Schirmer-I test (without anaesthesia);
- Permanence of Lubricin on the Ocular Surface Tear film break-up time (TBUT);
- Best corrected distance visual acuity (BCVA);
- SANDE questionnaire scores – discomfort improvement entity;
- SANDE questionnaire scores – discomfort improvement speed;
- Signs evaluated by Slit lamp examination (SLE) (blepharitis, eyelid hyoeremia/oedema, lashes, conjunctiva hyperemia);
- Intraocular pressure (IOP);
- Corneal sensitivity by Cochet-Bonnet aesthesiometry.

7.2 PK parameters

- Lubricin concentrations in tears.

7.3 Safety and tolerability parameters

- Treatment-emergent adverse events (TEAEs), assessed throughout the study;
- Device deficiencies;
- External ocular examination;
- Review of ocular medical condition;
- Review of systemic medical condition.

8 STATISTICAL METHODS

The data documented in this study will be listed by subject, treatment, eye (enrolled eye(s), left and right) and evaluation time point, i.e. Baseline or Day 1 (Visit 1), Day 15 ±2 (Visit 2) and follow-up (Visit 3).

Appropriate descriptive statistics will be used according to the nature of the variable.

Not available data will be evaluated as “missing values”. The statistical analysis will be performed using SAS® version 9.3 (TS1M1) for Windows® (6) or higher.

8.1 Tables, listings and figures layout

Tables, listings and figures will be provided according to the following settings:

- Background: White
- Foreground: Black
- Font face: Times
- Font style: Roman
- Font size: 10 pt
- Font weight: Medium (data, footers and notes), Bold (titles and headers)
- Font width: Normal
- Layout: Landscape
- Top Margin: 1.3 cm
- Bottom Margin: 1.3 cm
- Left Margin: 2 cm
- Right Margin: 2 cm
- Test labels: Lubricin 20 µg/mL, Lubricin 50 µg/mL
- Control label: Vismed® 0.18%
- Date format: ddMMMyyyy
- Means, standard deviations, percent coefficient of variations, medians, lower confidence limits and upper confidence limits will be rounded to one digit more than the original data
- Minima and maxima will keep the same number of decimal digits as the source values
- p-values will be rounded to the fourth decimal digit and will be flagged by an asterisk (*) in case of statistical significance (i.e. p-value < 0.05 or, in case of centre by treatment interaction, p-value < 0.10)
- p-values lower than 0.0001 will be reported as "<.0001 *".

The data and results of Lubricin 20 µg/mL and Lubricin 50 µg/mL will be presented before the data and results of Vismed® 0.18% in all listings and tables.

8.2 Analysis sets

8.2.1 Definitions

A subject will be defined as screened after the signature of the informed consent, regardless of the completion of all the screening procedures.

A subject will be defined as randomized in the study if he/she is assigned to a treatment arm (Lubricin 20 µg/mL and Lubricin 50 µg/mL or Vismed® 0.18%).

- **Enrolled Set:** all enrolled subjects. This analysis set will be used for demographic, baseline and background characteristics
- **Full Analysis Set (FAS):** all randomized subjects, who receive at least one dose of the ID. This analysis set will be used for the efficacy analysis
- **Safety Set:** all subjects who receive at least one dose of the investigational medicinal product(s). This analysis set will be used for tolerability and safety analyses

Each subject will be coded by the CRO Biometry Unit as valid or not valid for the Enrolled set, FAS and Safety set. Subjects will be evaluated according to the treatment dose they actually received.

8.2.2 Reasons for exclusion from the Full Analysis Set

According to ICH E9 guideline (3), the reasons for exclusion of subjects from the Full Analysis Set are the following:

- failure to take at least one dose of the IDs;
- lack of any efficacy data post enrolment;
- failure to satisfy inclusion/exclusion criteria (eligibility violations). Subjects who fail to satisfy an inclusion/exclusion criterion may be excluded from the analysis without the possibility of introducing bias only under the following circumstances:
 - the entry criterion was measured prior to randomization;
 - the detection of the relevant eligibility violations can be made completely objectively;
 - all subjects receive equal scrutiny for eligibility violations;
 - all detected violations of the particular entry criterion are excluded.

8.2.3 Reasons for exclusion from the Safety Set

Reason for exclusion of subjects from the Safety Set is the following:

- failure to take at least one dose of the IDs.

8.3 Hypothesis tests

This is an exploratory investigation and no regulatory claim will be based on the results of this investigation.

The aim of the investigation is just to collect preliminary data in order to evaluate tolerability, safety, permanence on the ocular surface and efficacy of two concentrations of Lubricin (20 and 50 µg/mL) eye drops versus sodium hyaluronate (HA) 0.18% eye drops (Vismed®) in patients with ocular discomfort following refractive surgery.

No formal hypothesis test will be performed in order to compare the two concentrations of Lubricin (20 and 50 µg/mL) eye drops versus sodium hyaluronate (HA) 0.18% eye drops (Vismed®).

8.4 Sample size and power considerations

The expected mean VAS changes, the expected standard deviations and the expected proportions of subjects reporting at least one TEAE throughout the study used for the sample size calculation are not based on any clinical result or literature data since this information is not available for the comparison of the two concentrations of Lubricin (20 and 50 µg/mL) eye drops versus sodium hyaluronate (HA) 0.18% eye drops (Vismed®) in patients with ocular discomfort following refractive surgery.

Due to the exploratory nature of the investigation, the sample size calculation is based on the confidence interval precision of the difference in the expected mean VAS changes and of the difference in the expected proportions of subjects reporting at least one TEAE throughout the study; the confidence level α is set to 0.05 for all the confidence intervals without any formal adjustment for multiplicity.

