7.2 Sample Size

As the primary objective of this study is to evaluate the tolerability and safety of Lubricin (20 and 50 µg/mL) eye drops solution administered over 2 weeks in patients with ocular discomfort following ocular refractive surgery, sample size was calculated based on clinical feasibility and no formal sample size calculation has been performed.

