1.1 Changes with respect to the investigational plan

The following changes were introduced into the SAP with respect to the clinical investigational plan (5):

- The tears collection for Lubricin dosing was insert as PK endpoint;
- The device deficiencies, external ocular examination, review of ocular medical condition and review of systemic medical condition were reported as safety and tolerability parameters.

These changes do not affect the principal features stated in the investigational plan and thus do not have to be documented in a protocol amendment.

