8.4.1 Confidence interval precision of the difference in the expected mean VAS changes

Supposing to have a value of -20 mm for all the mean VAS changes (dryness, foreign body sensation, burning/stinging, itching, pain, stick feeling, blurred vision and photophobia) and a standard deviation σ of 10 mm (the 50% of the expected mean VAS change) in the Lubricin 20 µg/mL arm, Lubricin 50 µg/mL arm and Vismed® 0.18% arm, the number of subjects per treatment arm required in order to have a two-sided 95% confidence interval of the difference in means with a precision ω (defined as the length of the confidence interval divided by two) of 9 mm can be calculated according to the following formula (7):

$$N_{\text{per arm}} = \text{ceiling} \left(\frac{2 \sigma^2 z^2_{1-\frac{\alpha}{2}}}{\omega^2} \right)$$

α (2-sided)	ω (precision)	σ	$N_{\text{per arm}}$
0.05	9 mm	10 mm	10

8.4.2 Confidence interval precision of the difference in the expected proportions of subjects reporting at least one TEAE throughout the study

Supposing to have a proportion of subjects reporting at least one TEAE throughout the study of 0.15 (i.e. 15%) in the Lubricin 20 µg/mL arm (π_{T1}) and in the Lubricin 50 µg/mL arm (π_{T2}) and of 0.45 (i.e. 45%) in the Vismed® 0.18% arm (π_C), the number of subjects per treatment arm required in order to have a two-sided 95% confidence interval of the difference in proportions with a precision ω (defined as the length of the confidence interval divided by two) of 0.4 (i.e. 40%) can be calculated according to the following formula (8):

$$N_{per\ arm} = ceiling\left(\frac{z^2_{1-\frac{\alpha}{2}} [\pi_{T_j}(1-\pi_{T_j}) + \pi_C(1-\pi_C)]}{\omega^2}\right)$$

α (2-sided)	ω (precision)	π_{T_1}, π_{T_2}	π_C	$N_{per\ arm}$
0.05	40%	15%	45%	10

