8.11 Efficacy analysis

8.11.1 Primary efficacy analysis

The primary efficacy analysis will be performed on the subjects included into the Full Analysis Set.

Subjects will be analysed according to the treatment they actually received.

8.11.1.1 Tolerability using a Visual Analogue Scale (VAS) for dryness, foreign body sensation, burning/stinging, itching, pain, stick feeling, blurred vision and photophobia

The VAS values of each ocular symptom (i.e. dryness, foreign body sensation, burning/stinging, itching, pain, sticky feeling, blurred vision and photophobia) and their changes from day 1 - pre-dose values and day 15±2 - pre-dose values for the study/primary eye and for the non-study/secondary eye will be listed ([Listing 16.2.6.1](#)) and summarised by treatment and time point using descriptive statistics (mean, SD, CV%, minimum, median and maximum) ([Table 14.2.1.1](#)).

The VAS values of each ocular symptom for the study/primary eye and for the non-study/secondary eye will be analysed using an analysis of variance for repeated measures model. The model will include fixed effect terms for time point, baseline covariate (i.e. the day 1 - pre-dose value) and treatment. Time point will be specified as a repeated measurement. An unstructured covariance structure of the R matrix will be used and covariance parameters will be estimated using the restricted maximum likelihood method ([Table 14.2.2.1](#)).

Only the VAS values collected at Visit 1, Visit 2 and Visit 3 will be included into the analysis of variance for repeated measure model.

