8.12.1 Adverse events

Adverse events (AEs) will be coded by System Organ Class (SOC) and Preferred Term (PT), using the Medical Dictionary for Regulatory Activities (MedDRA) version 20.1.

AEs will be classified as pre-treatment AEs (PTAEs) and treatment-emergent AEs (TEAEs), according to the period of occurrence, as follows:

- PTAEs: all AEs occurring before the first dose of the ID and not worsening after the first dose of the ID
- TEAEs: all AEs occurring or worsening after the first dose of the ID

Individual PTAEs and TEAEs will be listed by treatment ([Listing 16.2.7.1](#), [Listing 16.2.7.2](#)).

No summary table will be provided for PTAEs.

TEAEs will be summarised by treatment and overall.

- The number and percentage of subjects with any TEAE and the number of TEAEs will be presented overall ([Table 14.3.1.1](#)) and by SOC and PT ([Table 14.3.1.2](#));
- The number and percentage of subjects with any TEAE by relationship and the number of TEAEs by relationship will be presented ([Table 14.3.1.1](#));
- The number and percentage of subjects with any TEAE by intensity and the number of TEAEs by intensity will be presented overall ([Table 14.3.1.1](#)) and by SOC and PT ([Table 14.3.1.3](#));
- The number and percentage of subjects with any TEAE related to the ID ([Table 14.3.1.1](#)) and the number of TEAEs related to the ID will be presented overall and by SOC and PT ([Table 14.3.1.4](#));
- The number and percentage of subjects with any TEAE leading to discontinuation and the number of TEAEs leading to discontinuation will be presented ([Table 14.3.1.1](#)).

Serious TEAEs will be summarised by treatment and overall.

- The number and percentage of subjects with any Serious TEAE and the number of Serious TEAEs will be presented overall ([Table 14.3.1.1](#)) and by SOC and PT ([Table 14.3.1.5](#));
- The number and percentage of subjects with any Serious TEAE by relationship and the number of Serious TEAEs by relationship will be presented ([Table 14.3.1.1](#));
- The number and percentage of subjects with any Serious TEAE related to the ID and the number of Serious TEAEs related to the ID will be presented overall and by SOC and PT ([Table 14.3.1.6](#));
- The number and percentage of subjects with any Serious TEAE leading to discontinuation and the number of Serious TEAEs leading to discontinuation will be presented ([Table 14.3.1.1](#)).

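### The SAP justifies 10 per arm by two between-arm confidence intervals that no visible analysis section specifies, and its VAS model as listed cannot give a Day 15 difference

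*SAP*

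**What the plan says.** **Sample size.** Protocol 7.2 states that "sample size was calculated based on clinical feasibility and no formal sample size calculation has been performed". SAP 8.4 nevertheless presents a calculation: "the sample size calculation is based on the confidence interval precision of the difference in the expected mean VAS changes", together with the matching interval for the proportion of subjects with at least one TEAE. SAP 8.4.1 seeks a two-sided 95% interval for the difference in means "with a precision ω (defined as the length of the confidence interval divided by two) of 9 mm". SAP 8.4.2 seeks a half-width of 40 percentage points for the TEAE difference. Each gives 10 per arm. SAP 1.1 lists the departures from the protocol, for example "The tears collection for Lubricin dosing was insert as PK endpoint", but not this one.

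**VAS analysis.** SAP 8.11.1.1 plans descriptive statistics by arm and time point, then a repeated-measures model: "The model will include fixed effect terms for time point, baseline covariate (i.e. the day 1 - pre-dose value) and treatment". On the data used it says "Only the VAS values collected at Visit 1, Visit 2 and Visit 3 will be included". No contrast, time point for a contrast, or confidence interval is named. SAP 4.5.1 says that during follow-up, from Day 15 to Day 22, "any ocular topical treatments are allowed, including other artificial tears/lubricants as prescribed by the treating physician".

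**TEAE analysis.** SAP 8.12.1: "The number and percentage of subjects with any TEAE and the number of TEAEs will be presented overall", with further breakdowns of the same kind. No difference between arms and no interval is mentioned.

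**The concern.** The stated purpose of the sample size and the stated analyses do not meet. SAP 8.3 plans no formal comparison of Lubricin with Vismed. The difference of each Lubricin arm from Vismed, with its interval, would therefore be the main comparative information on the two primary endpoints. The visible method text commits to neither interval.

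The VAS model adds a second problem. Without a treatment-by-time term it forces the same treatment difference at every time point. A Day 15 least-squares difference taken from it would simply equal that common effect, which also draws on Visit 3, when subjects may be using other drops. Protocol 7.1.4 asks for the time profile of treatments, and a model that imposes parallel profiles cannot show one by arm. The secondary endpoints in SAP 8.11.4 are compared at Day 15 pre-dose; the primary VAS endpoint is not.

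**Working it through.** **1. The plan's own figures reproduce.** Inputs from SAP 8.4.1 and 8.4.2: two-sided 95%, SD 10 mm, half-width 9 mm; TEAE proportions 0.15 and 0.45, half-width 0.40.

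- Means: 2 × 10² × 1.96² / 9² = 9.49, rounded up to 10.
- Proportions: 1.96² × (0.15 × 0.85 + 0.45 × 0.55) / 0.40² = 1.96² × 0.375 / 0.16 = 9.003, rounded up to 10.

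The TEAE half-width at 10 per arm is 1.96 × √(0.375/10) = 0.38, inside the stated 0.40.

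**2. What the listed VAS model estimates.** With no interaction, the treatment effect is a weighted mean of the time-specific differences, with weights S⁻¹1 / (1′S⁻¹1), where S is the covariance matrix of the responses. For two responses (Day 15 pre-dose and Visit 3), let k be the ratio of the Visit 3 SD to the Day 15 SD and ρ their correlation. The Day 15 weight is (k² − ρk) / (1 + k² − 2ρk). The SAP gives neither k nor ρ, so the values below are assumptions.

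| k | ρ = 0.3 | ρ = 0.5 | ρ = 0.7 |
|---|---|---|---|
| 0.8 | 0.345 | 0.286 | 0.154 |
| 1.0 | 0.50 | 0.50 | 0.50 |
| 1.25 | 0.655 | 0.714 | 0.846 |

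At k = 1, a 9 mm difference at Day 15 that is absent at Visit 3 is estimated as 0.5 × 9 = 4.5 mm. Simulating the listed model in that case (10 per arm, SD 10 mm, ρ = 0.5, true difference −9 then 0, 1,500 runs) gave a mean estimate of −4.64 mm (simulation SE 0.11).

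The text does not say whether the 15- and 30-minute post-dose readings are responses. If all six post-baseline readings enter with equal variances and correlations, Day 15 pre-dose has weight 1/6.

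**3. Precision at one time point, unadjusted.** The half-width is q × 10 × √(2/n). Protocol 7.3 expects 10% drop-out and Protocol 6.1.5 rules out replacement, so 9 per arm is shown as well.

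| n per arm | z | t, three arms pooled | t, two arms |
|---|---|---|---|
| 10 | 8.77 | 9.18 (27 df) | 9.40 (18 df) |
| 9 | 9.24 | 9.73 (24 df) | 9.99 (16 df) |

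**4. With baseline adjustment.** The half-width becomes t × 10 × √(2/n) × √(1 − r²), where r is the correlation with baseline. Average chance baseline imbalance multiplies it by √(1 + 1/25) for n = 10 (26 df) and √(1 + 1/22) for n = 9 (23 df).

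- r = 0: 9.37 mm (n = 10) and 9.97 mm (n = 9).
- r = 0.3: 8.94 mm and 9.51 mm.
- r needed to reach 9 mm: about 0.20 (no imbalance) to 0.28 (average imbalance) for n = 10, and 0.39 to 0.43 for n = 9.

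The SAP states no value for r.

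**The case against.** - **Intervals may be planned out of sight.** The SAP appendices are redacted, and SAP 8.1 sets a rounding rule for confidence limits. This stands as a limit: the claim covers the visible text only. The rounding rule names no analysis.
- **The information is reported anyway.** Table 14.2.1.1 gives VAS means and SDs by arm and time point, and TEAE counts give the risk difference. A reader could compute both by hand. For VAS that yields only an unadjusted difference that nobody pre-specified, and it does not repair the model.
- **Day 15 is an inference.** SAP 8.4.1 names no time point. That is true. The two-week treatment objective and the Day 15 comparisons in SAP 8.11.4 support the inference, and the missing time point is part of the gap.
- **The halving is a scenario.** It needs a Day 15 difference that vanishes by Visit 3, and 9 mm is the planned half-width, not an expected effect; SAP 8.4.1 assumes equal changes in all arms. This stands. If six exchangeable readings enter, Visit 3 too has weight only 1/6, and most of the estimate comes from other on-treatment readings, four of them shortly after a dose.
- **The precision shortfall is trivial.** It is small beside the uncertainty in an SD that SAP 8.4 says has no data behind it, so it is a secondary point.
- **The trial is exploratory.** SAP 8.3 says so. That limits the consequences, but it makes estimates with intervals more important, and SAP 8.4 itself chose that framework.

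**Conclusion.** The concern holds. In the visible text, neither interval that justifies the sample size is specified as an analysis, and the listed VAS model cannot yield an end-of-treatment difference. How far its treatment effect departs from the Day 15 difference depends on covariances the plan does not give: the Day 15 weight is 1/2 with two equal-variance responses, 0.15 to 0.85 over the assumed SD ratios and correlations, and 1/6 with six exchangeable readings.

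The conflict between Protocol 7.2 and SAP 8.4 is real and is not listed in SAP 1.1. The 10 per arm and the TEAE precision are not in dispute. The 9 mm figure is slightly optimistic for an unadjusted difference at one time point; baseline adjustment could make up the gap.

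**What to change.** 1. In SAP 8.11.1.1, add a treatment-by-time term and list which VAS readings are responses. Report the model-based difference of each Lubricin arm from Vismed at Day 15 pre-dose with a 95% interval. Eight symptoms, two eyes and two contrasts make 8 × 2 × 2 = 32 intervals, so it would help to present the study/primary eye of SAP 8.6 as the main one.
2. In SAP 8.12.1, add the difference in the proportion with at least one TEAE, each Lubricin arm versus Vismed, with a 95% interval; a score interval suits these numbers.
3. Restate SAP 8.4 along these lines: *Ten per arm was chosen for feasibility. At an assumed SD of 10 mm, the 95% half-width for a difference in mean VAS change at one time point, before baseline adjustment, is about 9.2–9.4 mm with 10 evaluable per arm and 9.7–10.0 mm with 9. The reported interval is baseline-adjusted; the upper figures are a conservative guide to it.* The TEAE precision figure can stay.
4. List this in SAP 1.1 as a change from Protocol 7.2.

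**Cost.** SAP wording, one model term and a few table columns; no extra patients. The stated VAS precision becomes slightly less favourable. A Day 15 contrast is also wider than a two-visit average: at an assumed between-visit correlation of 0.5 and 10 per arm, 9.18 mm against 9.176 × √((1 + 0.5)/2) = 7.95 mm.
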